Adult patients with severe CRSwNP \pm asthma \pm AERD are recruited. Clinical baseline information of the patients is collected including smoking, allergy, asthma, medication, previous operations, co-morbidities, duration of symptoms. During preoperative visit/s in the ENT clinic nasal medication including treatment of exacerbations during the previous year is recorded. Medication for asthma during the previous year is counted and emergency care visits for airway symptoms/asthma attacks, hospitalizations, and other visits for asthma are monitored.

Preoperatively the patients undergo endoscopy (35) and (CB)CT. Polyps are scored on a 0-4 scale on each side and a Lund-Mackay computer tomography score (LM CT score, range, 0-24) is obtained (30, 31). Quality of life data and data for cost analysis are collected by validated questionnaires: Sinonasal outcome test (SNOT-22), generic HRQoL questionnaires (15D, EQ-5D-5L). Work Productivity and Activity Impairment Questionnaire: General Health (WPAI:GH), Productivity Costs Questionnaire (iPCQ), Medical Consumption Questionnaire (iMCQ) and asthma control tests (ACT,

miniAQLQ). The patients undergo spirometry with bronchodilatation and PEF (2 weeks as a diagnostic test, 1 week in follow-up with patients own medication).

Figure 1.

Inclusion criteria: Patients having uncontrolled CRSwNP and not responding to medical treatment are asked to participate in the study. Conservative treatment consists of corticosteroid drops and nasal lavage lasting at least 3 months before surgery is considered. Uncontrolled CRSwNP is defined as high polyp grade (≥ 4 , bilateral), and SNOT-22 ≥ 30 , and high CT Lund-Mackay score (LM score ≥ 14). In addition, patient should have a history of at least one of

the following: ≥ 1 previous surgeries for CRSwNP; ≥ 1 oral corticosteroids during the past two years; ≥ 3 antibiotic courses during the past two years. In patients with contraindication/adverse effects in using oral steroids additional criteria are not required.

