Exclusion criteria: Age < 18 years, age > 65 years, complication of CRS (f.e. mucocele, invasive fungal rhinosinusitis), other diagnosis than CRSwNP (inverted papilloma, antrochoanal polyp etc), previous external sinus surgery or Draf 3 procedure (or indication for external approaches or Draf 3, bleeding diathesis, pregnancy/ breastfeeding, cystic fibrosis, primary ciliary dyskinesia (PCD), sarcoidosis, granulomatosis with polyangiitis (GPA), eosinophilic granulomatosis with polyangiitis (EGPA), immunosuppression (diagnosed Specific Antibody Deficiency (SAD), CVI, HIV or use of biologicals/immunosuppressive medication), immunotherapy, daily use of systemic corticosteroids, communication problems (f.e. neurological/psychiatric disease, language skills), unlikely to comply, other severe disease, inability to be operated.

Randomization and surgery. The randomisation is performed by a professional statistician in blocks and for each center. The randomisation group of consecutive patients is sealed in numbered envelopes and kept in a locked room; the envelope is opened during the visit after informed consent. The patients are randomized for 1. total ethmoidectomy +sphenotomy +frontal opening (Draf2a) and 2. removal of polyps with uncinectomy, +/-opening of the natural ostium +/- ground lamella but not opening sphenoid or frontal sinus unless already opened in a previous surgery (Figure 1). Sinus operations are performed under general or local anesthesia on both sides with standard techniques and instrumentation by ENT specialists. Videoendoscopy is recorded at completion of extended surgery. Extended sinus surgery is usually performed with navigation. If not contraindicated, the patients may receive peroral corticosteroids 10-14 days perioperatively starting a few days before surgery.

Follow-ups. Patients are monitored before and during the follow-ups. The follow-ups are 3, 6, 9, 12,18 and 24 months postoperatively. During each visit the validated questionnaires and nasal endoscopy are performed. Nasal patency and olfaction as well as spirometry and PEF are monitored. Blood and tissue samples and low-dose sinus CT scans (1 year postop) are performed (Figure 1).

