We also monitor intra-operative factors (such as anesthesia method, use of local e.g. cocaine, terracortril and systemic medication, e.g. antibiotics and dexametasone, operation time and bleeding, use of tampons, complications, mucopurulent excretions, early postoperative factors such as duration of hospitalization, timing of tampon removal, duration of sick leave, medication, complications, visits and hospitalizations; as well as exacerbations, need of medication (po. corticosteroids; antibiotics). Time of surgery and equipment needed is recorded.

The primary end point is the change in SNOT-22 1 and 2 years postoperatively. Secondary end points include changes in polyp score, LM CT score, hrQOL, loss of productivity, nasal patency (peak nasal inspiratory flow (PNIF) +/- acoustic rhinometry (ARM), olfaction test (Sniffin' Sticks, identification), lung function (spirometry and PEF) and pathologic findings. Safety (complications, adverse effects) costs and loss of productivity between study arms will be compared. The study will compare costs of CRSwNP and asthma treatment one year before and two years after surgery. In addition to data from medical records and patients, data may be collected from national health records.

During and after follow-up, patients can undergo revision operation or other treatment, if needed and patients will still be followed for the duration of the study. Patient's disease control is monitored postoperatively by ENT-doctor as described earlier. Patients who have uncontrolled disease not responding to medication undergo CT scans and are evaluated for the need of removal of polyps and re-ethmoidectomy according to their study arm. In addition, AERD-patients are evaluated for their willingness in ASA desensitization and to participate in the AirGOs clinical trial.

B. Genome-scale search for biological key-factors

Peripheral blood, intranasal mucus and cell brushing samples, nasal polyp and/or nasal mucosal biopsies are taken from clinical trial participants and volunteer control subjects. The samples will be stored at Helsinki Biobank. These samples are collected in a time-series manner (pre-intervention, 24w post start of intervention) and biopsies are taken under local anesthesia. Nasal brushings and mucus swabs are collected from nasal mucosa, under middle turbinate, without local anesthesia. If possible, subjects are asked to be for 7-14 days without CRS medication before taking nasal specimens.

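### Baseline is not placed before allocation and follow-up is dated only from surgery: name a pre-envelope baseline, and follow randomised patients who are not operated

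*Combined protocol and SAP*

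**What the plan says.** All of this stands in section 3, Methods, A. Operative study, unless noted.

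- **Allocation.** The Randomization and surgery paragraph uses numbered sealed envelopes, and "the envelope is opened during the visit after informed consent". No interval between that visit and the operation is given, and the readable text describes no blinding.
- **Baseline.** "Preoperatively the patients undergo endoscopy (35) and (CB)CT". Medication history has a similar anchor: "During preoperative visit/s in the ENT clinic nasal medication including treatment of exacerbations during the previous year is recorded". In the same paragraph, "Quality of life data and data for cost analysis are collected by validated questionnaires", with SNOT-22, 15D, EQ-5D-5L, WPAI:GH, iPCQ, iMCQ, ACT and miniAQLQ named, followed by spirometry and PEF. None of these is placed before or after the envelope.
- **Eligibility.** "Patients having uncontrolled CRSwNP and not responding to medical treatment are asked to participate in the study". The definition begins "Uncontrolled CRSwNP is defined as high polyp grade" (at least 4, bilateral) and adds SNOT-22 of at least 30 and a Lund-Mackay score of at least 14.
- **Follow-up and primary end point.** "The follow-ups are 3, 6, 9, 12,18 and 24 months postoperatively", and "The primary end point is the change in SNOT-22 1 and 2 years postoperatively".
- **Continued follow-up.** The one sentence on this concerns patients who have a revision operation or other treatment. The Statistics paragraph later in section 3 names no analysis set and gives no rule for randomised patients who are not operated.

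**The concern.** The schedule is anchored on surgery at both ends, while the arm becomes known at randomisation.

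At the front end, a change score is safe from allocation effects only if its starting value was fixed before anyone could know the arm. A patient who knows which operation is coming may answer a questionnaire differently before anything has been done. A late preoperative value has a second weakness. The Randomization and surgery paragraph allows optional oral corticosteroids starting a few days before the operation, so one centre's baseline could be taken on treatment and another's off it.

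At the back end, a patient who is randomised and then cancels, or becomes unfit, never reaches a visit counted from surgery. The background section describes the extended operation as longer, more dependent on experience and navigation, and potentially more prone to complications. Failure to be operated may therefore differ between arms. Losing such patients is then an exclusion after randomisation that depends on the arm, and a SNOT-22 that was never collected cannot be recovered in the analysis.

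**Working it through.** **1. Order of events in the text.**

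- Before consent: polyp grade, SNOT-22 and Lund-Mackay score must exist, because only patients who meet these criteria are approached.
- At the visit after consent: the envelope is opened.
- Before surgery, otherwise undated: 15D, EQ-5D-5L, WPAI:GH, iPCQ, iMCQ, ACT, miniAQLQ, spirometry and possibly a repeat SNOT-22.
- After surgery only: every follow-up visit and both primary time points.

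The secondary baselines can therefore fall after allocation. For SNOT-22 the gap is narrower: a pre-allocation value exists but is not named as the baseline. A patient without an operation has no 12- or 24-month date.

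**2. The plan's own sample size.** Inputs from the Power calculation paragraph: difference 9, SD 20, alpha 0.05 (sidedness not stated), power 0.80, 10% loss. Two-sided normal approximation: n = 2 × (1.96 + 0.8416)² × 20² / 9² = 77.5, so 78 per arm. The t-test gives 78.5, so 79 per arm, as stated; one-sided gives 62 and does not fit. Then 158 × 1.10 = 173.8, so 174, as stated. The allowance is 174 − 158 = 16 patients, described only as loss to follow-up.

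**3. Unoperated patients with no primary value.** The documents give no rate, so the share u is assumed, on top of the 10% loss. Per arm, n = 174 × (1 − 0.10 − u) / 2, and power = Φ(9 / (20√(2/n)) − 1.96).

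| u (assumed) | n per arm | power |
|---|---|---|
| 0 | 78.3 | 0.804 |
| 2% | 76.6 | 0.795 |
| 5% | 74.0 | 0.781 |
| 10% | 69.6 | 0.756 |

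If such patients are instead kept in the analysis, and show no difference between arms, the contrast is diluted. At 5% it is 9 × 0.95 = 8.55, with power 0.763 at 78.3 per arm. Neither route gains power; the case for keeping them rests on bias.

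**4. A baseline shifted by knowledge of the arm.** The shift b is assumed. With no true effect, an unadjusted change score, SD 20 (taken to apply to the change) and 79 per arm, SE = 20√(2/79) = 3.18. Type I error = Φ(−1.96 + b/SE) + Φ(−1.96 − b/SE).

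- b = 1: 0.061
- b = 2: 0.096
- b = 3: 0.156

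With adjustment for that baseline and an assumed correlation r, the bias becomes r × b and the residual SD becomes 20√(1 − r²). For b = 3 and r from 0.3 to 0.5, the error is 0.060 to 0.085. These figures apply to SNOT-22 only if a value taken after the envelope is used as the baseline.

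**The case against.** Several objections are fair, and they mark how far the point goes.

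- **Eligibility values already exist.** A reader might infer that every change end point starts from a value reported after the arm is known. The inclusion criteria do not support that: SNOT-22, polyp grade and Lund-Mackay score are obtained before a patient is approached. What stands is that none of them is named as the baseline, and that the other questionnaires and spirometry have no such protection.
- **The plan does not drop unoperated patients.** A reader might infer from the surgical anchor that they are excluded. No sentence says so; the text is silent. Inability to be operated is an exclusion criterion, which removes patients known to be unfit at screening. It does not cover those who cancel or become unfit after the envelope is opened.
- **PEF.** A reader might infer that the two-week PEF record must run past the envelope. The text calls it a diagnostic test, so it may belong to the work-up before consent. It gives no reason to delay the envelope.
- **Figure 1.** It is cited for the arms and the follow-ups and is not shown. It may set the order of visits. A schedule alone would still not give an analysis rule for unoperated patients.
- **Knowledge of the arm.** The text does not say that the patient is told when the envelope is opened, or how long the wait for surgery is. With no blinding described, it does not prevent this either.
- **Adjustment and choice of outcome.** The Power calculation paragraph refers to a postoperative difference, which a baseline shift does not move, and the Statistics paragraph promises covariate adjustment without naming baseline. Either would reduce the effect in step 4, but the primary end point as defined is a change.

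Dating visits from surgery is a reasonable choice for patients who are operated.

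**Conclusion.** The point holds in a limited form, as an inexpensive improvement worth making. In the readable text, baselines not used for eligibility may be recorded after allocation, the baseline SNOT-22 for the primary change is not identified, and a randomised patient who is never operated has no defined primary assessment. The last gap matters most, because it decides which data are collected and the loss may depend on the arm.

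The documents give neither the share of unoperated patients nor the size of any baseline shift, so no bias can be derived from them. On the assumptions shown, 5% unoperated beyond the planned loss costs about 0.02 of power (0.80 to 0.78). A 2-point shift in an unadjusted change score would raise the type I error from 0.05 to about 0.10. The stated sample size reproduces and needs no correction on this account.

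**What to change.** 1. State that all baseline questionnaires and measurements are completed after consent and before the envelope is opened, except those already obtained for eligibility. Define baseline SNOT-22 as the last value before opening. Values repeated nearer to surgery may be kept but are not the baseline. The envelope need not wait for a PEF record.
2. State that randomised patients who are not operated are sent SNOT-22, on the paper or electronic questionnaire already in use, at 12 and 24 months from randomisation, or from the scheduled operation date where one exists. Analyse them in their randomised arm, with the same dating rule in both arms.
3. If Figure 1 already fixes the visit order, repeat that order in the text and check that it agrees with item 1.

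Cost: a little more work at the consent visit, questionnaire follow-up of a few extra patients (5% of 174 would be about 9), and slight dilution of the contrast. At an assumed 5% unoperated, that means 8.55 instead of 9 points and power near 0.76, against 0.78 if the same patients were left out. That is a small price for a comparison that keeps the randomised groups intact.

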This is a randomized controlled multicenter study that focuses on severe CRSwNP \pm asthma \pm AERD. Our primary objectives of this study are to find out:

- (1) Does extended surgery (total ethmoidectomy with opening of large sinuses) reduce HRQoL more effectively than partial ethmoidectomy? The primary end-point is the disease-specific questionnaire SNOT-22. The secondary objectives are to:
 - 1) Evaluate the outcome of surgery on polyp size, symptoms, general HRQoL, asthma specific HRQoL, olfaction, nasal patency, revision-rate, exacerbation-rate, lung function, costs and safety
 - 2) Develop the care pathway of CRS+/-asthma+/-AERD patients to improve outcomes and cost effectiveness of treatment
 - 3) Develop safe, specific and sensitive genome-based biomarkers for detection and management models for of severe airway inflammation and to further develop markers for progressive disease forms.
 - 4) To see if patients with certain genetic and/or clinical predispositions will benefit from extended surgery.

Significance: The clinical significance of this study is to develop cost-effective treatment models that will facilitate risk-estimation and prevention of the onset and the progression of severe CRSwNP, asthma and AERD. The potential societal impact is that it reduces the burden of inflammatory airway diseases. It will increase co-work between

clinicians, standardize treatment protocols and increase equality in health care in Finland. The academic impact is to train PhD students and clinicians. We will publish in peer reviewed international open access medical journals.

3. Methods

A. Operative study

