The study is performed as a randomized prospective controlled multicenter trial. A total of 174 adult severe CRSwNP patients \pm asthma \pm AERD participate in the study. The patients are recruited at the Departments of Otorhinolaryngology and Head and Neck Surgery, Helsinki University Hospital (HUH) (n=60-80), Tampere University Hospital (TUH) (n=20), Kuopio University Hospital (KUH) (n=15), Oulu University Hospital (OUH) (n=20) and Turku University Hospital (Tyks) (n=15). Otorhinolaryngological department of the Academic Medical Center, AMC, Amsterdam will recruit 60-80 patients for the study. Patients refusing to participate in the study are asked to contribute with HRQoL data, and age and gender are recorded. The study will be monitored by a professional monitor. Electronic CRF and paper/electronic patient questionnaires provided by HUS will be used (eCRF and patient questionnaires, Granitics).

Power calculation: The mean postoperative difference in the Sinonasal Outcome test (SNOT-22) was assumed to be at least 9 between the treatment arms. In a previous study the response within each subject group was normally distributed with standard deviation 20. If the true difference in the experimental and control means is 9, we will need to study 79 experimental subjects and 79 control subjects to be able to reject the null hypothesis that the population means of the experimental and control groups are equal with probability (power) 0,8. The Type I error probability associated with this test of this null hypothesis is 0,05. Taking into account the patients lost to follow-up, 10%, the number of patients needed to recruit is 174.

The diagnosis of CRS with nasal polyps (NP) is based on positive history, nasal endoscopy and computed tomography scans (EPOS 2012). EPOS-criteria for CRS include: Inflammation of the nose and the paranasal sinuses characterised by two or more symptoms, one of which should be either nasal blockage/obstruction/congestion or nasal discharge (anterior/posterior nasal drip): \pm facial pain/pressure, \pm reduction or loss of smell.

[figure not shown]
The diagnosis of asthma is based on spirometry, methacholine or histamine challenge and peak expiratory flow (PEF). Allergy is verified with positive history and skin prick test or specific igE. AERD is verified by typical history.

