Statistics. Data analysis will be carried out on the relationship between two operative treatments, and between ASA- and placebo desensitization. Variables tested in the statistical models include age, gender, exposures, infections, diseases, symptoms, exacerbation-rate, satisfaction, image-findings, endoscopic findings, operation, perioperative factors (such as operation time), complications, sick leave, biological factors (predisposing SNPs, alterations in transcriptome or microbiome), occupation, asthma, grade of nasal polyps, AERD, allergy, revision-rate, side-effects of AD, hospitalizations, sick leaves, and other factors at different time-points. We will use several software: R 3.0.2, SPSS 22.0 Statistical Software Package (SPSS, Chicago, IL) and STATA (Release 13.1 software, StataCorp, Texas, USA). For comparisons, the results will be analyzed by Logistic regression, Student's t-, Chi-square, (nonparametric) Fisher's exact and Mann Whitney U test, Cox's proportional-hazards model, cumulative hazard function H(t), hazard ratio, Kaplan–Meier method, and log rank test. Genetic calculations on Hardy–Weinberg equilibrium and linkage disequilibrium will be performed with Arlequin (version 3.5) using SPSS Statistics (version 20.0, IBM). P-values less than 0.05 are considered statistically significant. Results of logistic regression are reported as odds ratios (OR) with 95% confidence intervals. All models will be adjusted by selected covariates (potential confounding factors).

4. Implementation of the study plan

The **operative** trial will be performed during the years 1-5, starting in September 2018. The wetlab will be performed during the years 2-6. The statistical analyses, data management, search for literature, and manuscript(s) will be performed during the years 1-6.

5. The study group and collaborators

The study group:

Docent, Otorhinolaryngologist (HUH) [name] is director and is responsible for the management of the project and conducts the AirGOs Operative study in ENT hospital of HUH.

Docent, Pulmonologist (HUH) [name], is vice-director and conducts pulmonological assessment in Skin and Allergy Hospital (HUH/IAS).

MD, PhD, Otorhinolaryngologist (HUH) [name], is vice director and performs operative and clinical study in ENT Hospital

Docent [name] (HUH) performs in IAS and conducts data management, manuscripts and sample studies

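### The primary end point is SNOT-22 change at both 1 and 2 years with no rule linking them; tested unadjusted, the stated 0.05 error and 0.8 power are not both delivered

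*Combined protocol and SAP*

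**What the plan says.** Four places in the combined protocol and SAP bear on this.

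- **Section 2 (Aims and significance)** gives no time point: "The primary end-point is the disease-specific questionnaire SNOT-22".
- **Section 3.A, end points**, gives two: "The primary end point is the change in SNOT-22 1 and 2 years postoperatively".
- **Section 3.A, Power calculation**, is written for a single comparison and names no year: "The mean postoperative difference in the Sinonasal Outcome test (SNOT-22) was assumed to be at least 9 between the treatment arms". The error rate is also set for one test: "The Type I error probability associated with this test of this null hypothesis is 0,05".
- **Statistics paragraph (end of section 3)** is a list of methods: "the results will be analyzed by Logistic regression, Student's t-, Chi-square, (nonparametric) Fisher's exact and Mann Whitney U test", followed by time-to-event methods. Its threshold is general: "P-values less than 0.05 are considered statistically significant". It also says that models will be covariate-adjusted.

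None of these gives an order of testing, a division of alpha, an either-or-both rule, a repeated-measures model or an averaged contrast. Figure 1 and some pages were not available to me, but the sections where such a rule would belong were.

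**The concern.** A primary end point read at two times needs a rule that turns two results into one verdict. Without it, the error rate and power stated in the sample size section belong to a test that the end point section does not define.

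The two plain readings fail in opposite ways. If a significant result at either year is enough, there are two chances of a false positive and the type I error exceeds 0.05. If both years must be significant, the error is not inflated but the chance of success falls below 0.8. These are alternatives and do not occur together.

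The practical risk is a split result, with one year significant and the other not. The investigators could then choose the favourable year after seeing the data. A split is realistic here: besides chance, section 3.A allows revision surgery or other treatment during follow-up with patients still followed, so the two years could truly differ.

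**Working it through.** **Inputs from the Power calculation.** Difference 9. SD 20: "the response within each subject group was normally distributed with standard deviation 20". Alpha 0.05. Power 0.8, for a null of equal means: "reject the null hypothesis that the population means of the experimental and control groups are equal with probability (power) 0,8". 79 per arm, 10% loss, 174 recruited.

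**Assumptions that are mine.** The difference of 9 and SD of 20 apply to the change in SNOT-22 at each year; the plan does not say whether the SD refers to postoperative scores or to change. The correlation r between the two test statistics is not in the documents, so I show 0.5 to 0.9.

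**Step 1: reproduce the plan's figure.** For one two-sided test, n = 2(1.96 + 0.842)² × 20² / 9² = 77.5, so 78 per arm. The exact t-test gives 79, with power 0.803. A one-sided test would give 62, so the plan is two-sided. Then 158 × 1.1 = 173.8, so 174. The sample size is right for one comparison.

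**Step 2: noncentrality at 79 per arm.** δ = 9 / (20√(2/79)) = 9 / 3.182 = 2.828. Single-test power by the normal approximation is 0.807.

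**Step 3: two unadjusted tests.** Let (Z₁, Z₂) be bivariate normal with unit variances and correlation r.

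- Either year, type I error: P(|Z₁| > 1.96 or |Z₂| > 1.96) with both means 0.
- Both years, power: P(Z₁ > 1.96 and Z₂ > 1.96) with both means δ.
- Split result: P(at least one significant) − P(both significant), with both means δ. At r = 0.7 this is 0.892 − 0.722 = 0.170.
- n for both years: the smallest n giving both-years power of 0.80 with δ = 9 / (20√(2/n)).

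| r | Either year at 0.05: type I error | Both years at 0.05: power | Exactly one year significant | Evaluable per arm for both-years power 0.80 |
|---|---|---|---|---|
| 0.5 | 0.0907 | 0.697 | 0.220 | 97 |
| 0.7 | 0.0835 | 0.722 | 0.170 | 93 |
| 0.8 | 0.0781 | 0.738 | 0.139 | 91 |
| 0.9 | 0.0704 | 0.758 | 0.098 | 87 |

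Simulation with t-tests (200,000 trials per setting) agrees within 0.01; both-years power is 0.689, 0.714, 0.730 and 0.753. The per-arm sizes in the last column are normal approximations and fall one or two patients short under the t-test.

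**Step 4: rules the plan could have stated.** For the average of the two years, the noncentrality is δ / √((1 + r)/2). At r = 0.7 this is 2.828 / 0.922 = 3.067.

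| r | 0.025 per year, success at either: type I error | Same rule: power | One averaged contrast at 0.05: power |
|---|---|---|---|
| 0.5 | 0.0465 | 0.859 | 0.904 |
| 0.7 | 0.0430 | 0.827 | 0.866 |
| 0.8 | 0.0402 | 0.807 | 0.846 |
| 0.9 | 0.0362 | 0.782 | 0.827 |

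So 79 per arm can support both stated figures under a suitable rule: the averaged contrast throughout this range, or the split alpha up to r of about 0.8. One named year at 0.05 also does so, by Step 1.

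**The case against.** The strongest reply is that this is an omission, not a failed calculation. The plan never says that two unadjusted tests decide the trial. Both the end point and the test are written in the singular, the arithmetic is right for one test, and a single-year or averaged reading would deliver 0.05 and 0.8. The 0.05 threshold in the Statistics paragraph covers all analyses, including the genetic ones, and is not a rule for primary success. That paragraph also mentions regression models, covariate adjustment and factors at different times, so a pair of plain t-tests is not the declared primary analysis. The percentages rest on an undocumented correlation and on equal effects at both years, and at r = 0.9 they are modest.

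Much of this stands. The sample size is correct for one comparison, the failure is confined to the two unadjusted readings, and its size depends on r. But the list of models supplies no link between the years, and a single-year or averaged reading has to be brought in from outside the text. The direction holds for any r below 1. Even at 0.9, about one trial in ten would give a split result with no pre-specified verdict.

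**Conclusion.** The concern holds. The rule for the primary decision is undefined, and applying the plan's general threshold to both years fails one of its two stated design figures. Over r from 0.5 to 0.9, either-year success has a type I error of 9.1% falling to 7.0%; both-years success has power of 0.70 rising to 0.76. Both shortfalls shrink as r nears 1. These sizes assume a difference of 9 and SD of 20 for change at each year and 79 evaluable per arm. The finding that no rule is stated needs none of these assumptions, and that alone makes this a must-fix.

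**What to change.** Before any comparative outcome data are examined, and with the change dated, name one primary time point and test the other in fixed sequence. Suggested text:

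> Primary: change in SNOT-22 at 12 months, two-sided 0.05. Change in SNOT-22 at 24 months is tested at 0.05 only if the 12-month test is significant.

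The reverse order controls error equally well. A single pre-specified joint contrast over the two years is an acceptable alternative. State the chosen time point in the Power calculation, bring section 2 into line with it, and report both yearly estimates with confidence intervals whatever the tests show.

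The cost is two or three sentences. The 174 patients stay, and the 12- and 24-month visits are already scheduled. Section 4 gives a start in September 2018, so the state of data access should be recorded with the change. The price of the fixed sequence is that the second year cannot be claimed if the first fails. On the assumptions above, the chance of claiming both years is the same 0.70 to 0.76. If the investigators want power of 0.80 for a claim at both years, they need about 97 to 87 evaluable per arm, or about 216 to 194 recruited (2 × 97 / 0.9 and 2 × 87 / 0.9).
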